In study evaluating the efficacy and tolerability of a split-dose PGE-ELS plus bisacodyl and a regular diet, 187 patients were randomly assigned to receive either 3 L of PGE-ELS (n = 96; Group A) with a liquid diet on the day before colonoscopy, or 2 L of PGE-ELS, one tablet of bisacodyl, and a minimally restricted diet on the day before colonoscopy, and then 1 L of the same solution on the day of colonoscopy (n = 91; Group B). Colon cleansing was significantly better in Group B with regard to the overall quality of the preparation ($p < 0.05$). Compliance was significantly higher in Group B as evidenced by the lower number of patients who discontinued the preparation (4 vs. 15; $p = 0.02$) because of side effects such as nausea or vomiting. The degree of discomfort, adverse events, and willingness to retake the preparation were not significantly different between the groups. The authors concluded that colonic preparation with split-dose polyethylene glycol-electrolyte provided better quality colon cleansing and higher compliance, with less dietary restrictions, than preparation with whole-dose polyethylene glycol-electrolyte (*El Sayed et al., 2003*).

In a single-blind, active control, randomized study of 895 patients, Marmo et al. evaluated the degree of colon cleansing comparing split-dosage versus non-split-dosage of two different PEG volumes (low-volume PEG + ascorbic acid vs standard-volume PEG-electrolyte solution). Overall compliance was excellent (97%) for both preparation methods. PEG plus ascorbic acid produced the same degree of cleansing as standard-volume PEG-electrolyte solution (77% vs 73.4%, respectively, within the split-dosage group and 41.7% vs 44.3%, respectively, within the non-split-dosage group). Independently of PEG volumes, the split-dosage regimen produced markedly superior cleansing results over the same-day method (good/excellent 327/435, 75.2% vs 186/433, 43.0%, $P = .00001$). The degree of bowel cleansing affected both caecal intubation (failed intubation 11.7% with fair/poor preparation vs 1.2% with good/excellent preparation, $P = .00001$) and polyp detection rates (12.2% with fair/poor vs 24.6% with good/excellent preparation, $P = .001$). Aborted procedures were significantly more frequent in the non-split-dosage arm (21.2% vs 6.9%, odds ratio [OR] 3.60 [2.29-5.77], $P < .0001$ (*Marmo et al., 2010*).

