9.3 POPULATIONS FOR ANALYSES

The following populations will be used for the statistical analyses:

- Safety set: all patients who take the study preparation, even only partially. Patients will be analysed according to the study drug dose actually received.
- Modified Safety set: all patients who take the study preparation, even only partially, and who do not meet significant protocol violations that regard inclusion/exclusion criteria. Patients will be analysed according to the study drug dose actually received.
- PK population (only for the pharmacokinetic sub-study): all randomized patients who complete the mannitol treatment and have at least one PK assessment, regardless of the outcome of colonoscopy. Patients will be analysed according to the study drug dose actually received.
- Full Analysis Set (FAS): all randomized patients who take the study preparation, even only partially, undergo the colonoscopy, and have a BBPS available for at least one colon segment after standard washing and air insufflation for luminal distension. According to the Intention to Treat (ITT) principle, patients will be analysed according to the study drug dose assigned at randomization.
- Per protocol (PP): all randomized patients who meet the following criteria:
 - Treatment with the study drug completed.
 - Colonoscopy completed adequately in absence of pathological obstruction that prevents reaching the right colon, including the cecum (i.e. endoscope does not find obstacles other than faecal material) and without acute deterioration of general conditions causing procedure suspension.
 - Bowel cleansing assessment and gas measurement are available for all colon segments after standard washing and air insufflation for luminal distension.
 - No significant protocol violations that regard inclusion/exclusion criteria or that can condition evaluations.

Patients will be analysed according to the study drug dose actually received.

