9.4.1 ANALYSIS OF VARIABLES

Phase II - Dose finding

Efficacy

The appropriate mannitol dose to be used in the comparative non-inferiority phase (phase III) will be singled out at the end of dose-finding based on the following criteria:

- 75% or greater rate of adequate bowel cleansing.
- Rate of patients in safe conditions, defined as the absence of potentially dangerous levels of H₂ and CH₄ in each colon segment (right, between ileocecal valve and appendix or as close as possible to the ileocecal valve in case of obstacles that prevent reaching the valve; transverse, including flexures; and left at the sigmoidal-rectum junction, 15-25 cm from anal margin) after standard washing and air insufflation for luminal distension).
- Clinical judgment based on the caecal intubation rate, the incidence of adverse events, treatment adherence and acceptability (considering ease of use, taste and willingness to reuse the preparation).

Should two or all three doses prove to be equally safe and effective, the lowest dose will be selected for phase III of the study.

Descriptive statistics and Wald 95% CI of the proportion of patients with adequate bowel cleansing will be provided for each dose.

In addition, a logistic regression model will be applied to assess the influence of the two stratification factors (constipation in the two weeks before the start of preparation for colonoscopy and centre) on dose response. A patient is considered a responder if he/she presents adequate bowel cleansing. In case of unbalanced enrolment among centres, a pooling approach will be adopted.

A supportive stepwise logistic regression model will also be applied to assess the influence on dose response of potential prognostic factors (i.e. age and previous unsuccessful bowel cleansing procedures) in addition to the two stratification factors. Based on the results from this model, the need to modify the stratification factors for phase III will be evaluated and the study protocol amended, if needed.

No between-group comparisons will be performed. The decision on the dose to be selected for phase III will be made on the basis of descriptive statistics and corresponding 95% CIs and on the

results of the logistic regression models. Endpoints will be analysed on the PP population. Results from the FAS will be used as supportive.

Caecal intubation rate

Descriptive statistics and Wald 95% CI of the caecal intubation rate will be provided for each dose.

Adherence and acceptability

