Descriptive statistics and Wald 95% CIs of the following adherence and acceptability variables will be provided for each dose:

- Adherence
- NRS score for ease of use and taste
- Willingness to reuse the preparation

Phase II - Pharmacokinetic sub-study

The pharmacokinetic parameters (C_{max} , t_{max} , AUC_{0-t} , $t_{1/2}$) of each dose will be analysed descriptively on the PK population.

Phase III - Non-inferiority

Primary efficacy analysis

The proportion of patients with adequate bowel cleansing (BBPS total score ≥ 6 , score ≥ 2 for each segment) during colonoscopy after standard washing and air insufflation for luminal distension will be calculated to evaluate the non-inferiority of the test drug vs the standard drug.

Non-inferiority will be assessed by computing the two-tailed Wald 95% confidence interval (CI) of the difference between the two proportions $\pi_T - \pi_S$. Non-inferiority is met if the 95% CI does not cross the predefined non-inferiority margin $\Delta = -0.08$ and lies entirely to the right of the margin (i.e. non-inferiority will be demonstrated if the lower bound of the two-sided 95% CI of the difference is > -0.08).

The non-inferiority margin $\pi_T - \pi_S = -0.08$ corresponds to a relative risk $\pi_T/\pi_S = 0.906$ when the proportion of successes in the standard group is 0.85. Should the proportion of successes in the standard group be lower than 0.85, the non-inferiority margin will be adjusted in order to have a relative risk of at least 0.906 (e.g. if the proportion of successes observed in the standard group is 0.80, the non-inferiority margin $\pi_T - \pi_S$ will be set equal to $= -0.075$, corresponding to a relative risk equal to 0.906).

If the 95% CI of the difference lies completely to the right of 0, the test treatment can be considered superior to the standard treatment at a 5% significance level.

The Wald method for non-inferiority of proportions will be applied (*Dann RS, 2008*).

The analysis will be performed on both the FAS and PP populations. Results from both populations will have equal importance.

Secondary efficacy analyses

The analysis of secondary variables will be performed on the FAS. No between-group inferential analysis will be performed. Descriptive statistics and 95% CIs of the between-group differences will be applied on the following variables:

- Number, appearance, size, location and histological classification of neoplastic and inflammatory colorectal lesions detected

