- Adenoma detection rate
- Caecal intubation rate
- Ottawa bowel preparation scale

Confidence intervals for proportions will be calculated based on the Wald method.

Adherence and acceptability

The analysis of adherence variables will be performed on the FAS. No between-group inferential analysis will be performed. Descriptive statistics and Wald 95% CIs of the between-group differences will be applied on the following variables:

- Bowel Cleansing Impact review (BOCLIR) scales
- Adherence
- NRS score for ease of use and taste
- Willingness to reuse the preparation

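### Phase II prescribes Wald intervals where rates may lie near 100% and gives adherence no sound lead population; the phase III gas comparison has no interval for the difference

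*Combined protocol and SAP*

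**What the plan says.** **Interval method.** For phase II caecal intubation, Section 9.4.1 says: "Descriptive statistics and Wald 95% CI of the caecal intubation rate will be provided for each dose". For adherence, ease of use, taste and willingness to reuse it says: "Descriptive statistics and Wald 95% CIs of the following adherence and acceptability variables will be provided for each dose". Section 9.1 plans 50 patients per dose. Section 9.4.1 rests the dose decision "on the basis of descriptive statistics and corresponding 95% CIs", together with the logistic models. Caecal intubation, adherence and acceptability enter that decision through clinical judgment.

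**Population.** The phase II Efficacy text in Section 9.4.1 ends: "Endpoints will be analysed on the PP population. Results from the FAS will be used as supportive". Caecal intubation and adherence then follow under their own headings, with no population named. One PP criterion in Section 9.3 is "Treatment with the study drug completed"; others require an adequately completed colonoscopy and cleansing and gas data for every segment. For phase III the plan is explicit: "The analysis of adherence variables will be performed on the FAS". Phase III secondary variables, which include caecal intubation, are also on the FAS.

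**Gas.** Section 2.1 calls it relevant to compare new and current preparations on the proportion of patients with dangerous H₂ or CH₄ levels, and says this study will make that comparison for mannitol and PEG. Section 9.4.2 plans descriptive statistics, which Section 9.4 defines for categorical data as counts and percentages. For phase III adherence and acceptability, by contrast: "Descriptive statistics and Wald 95% CIs of the between-group differences will be applied on the following variables". Secondary efficacy variables also get 95% CIs of the difference.

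**The concern.** A Wald interval takes its width from the estimated variance, which vanishes when every patient succeeds. It then reports complete certainty from 50 patients, although a true failure rate of up to 7.1% is compatible with 50/50. Caecal intubation could plausibly lie in that region, and those choosing the dose are told to look at the intervals.

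Adherence is one of the inputs that should help separate the three doses. If it is led by a set that admits only completers, it cannot do so. If no set is specified, the choice can be made after the data are seen.

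The gas outcome is the safety question that Section 2.1 gives as the reason mannitol fell out of use in Europe and the US. Two percentages side by side, without an interval, do not tell the reader how large an excess risk over PEG remains compatible with the data.

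**Working it through.** **1. The plan's own precision figures.** Section 9.1 uses 1.96 × √(p(1−p)/50). At p = 0.75, 0.80 and 0.85 this gives 12.0, 11.1 and 9.9 points, matching the stated ±12, ±11 and ±10. Exact Wald coverage at these rates with n = 50 is 94.1%, 93.8% and 94.1%. For the cleansing endpoint Wald is acceptable.

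**2. The same formula near 100%, n = 50.**

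| Successes | Wald 95% | Clopper-Pearson 95% | Wilson 95% |
|---|---|---|---|
| 50 | 100–100 | 92.9–100 | 92.9–100 |
| 49 | 94.1–101.9 | 89.4–99.9 | 89.5–99.6 |
| 47 | 87.4–100.6 | 83.5–98.7 | 83.8–97.9 |
| 46 | 84.5–99.5 | 80.8–97.8 | 81.2–96.8 |

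For 50/50 the Clopper-Pearson lower limit is 0.025^(1/50) = 92.9%.

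**3. How often this could happen for caecal intubation.** The plan states no expected rate, so one must be assumed. For PEG regimens, Section 2.1 reports "failed intubation 11.7% with fair/poor preparation vs 1.2% with good/excellent preparation"; for mannitol trials it reports a good or excellent share s of 66% to 90%. Combining the two, the true rate is p = 1 − [0.012s + 0.117(1−s)]. At s = 0.66 this is 1 − (0.0079 + 0.0398) = 0.9523; at s = 0.90 it is 1 − (0.0108 + 0.0117) = 0.9775. P(50/50) = p^50. Coverage is the sum of the binomial(50, p) probabilities of all counts whose interval contains p.

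| s | True rate | P(50/50) | Wald | Clopper-Pearson | Wilson |
|---|---|---|---|---|---|
| 0.66 | 95.2% | 8.7% | 91.1% | 99.1% | 96.9% |
| 0.75 | 96.2% | 14.2% | 85.5% | 98.8% | 95.8% |
| 0.85 | 97.2% | 24.5% | 75.3% | 98.8% | 95.0% |
| 0.90 | 97.7% | 32.1% | 67.9% | 99.5% | 97.4% |

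Section 2.1 also quotes 97% compliance for PEG regimens. If phase II adherence were at that level, Wald coverage would be 78.1%.

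**4. Adherence population.** There are two readings of the PP sentence.
- It covers all phase II endpoints. PP admits only patients who completed treatment, so adherence is 100% in every dose and only the supportive FAS result is informative.
- It covers efficacy only, the subsection it closes. Then no population is stated for phase II adherence.

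Either way, patients who took nothing appear in neither set, because the FAS requires at least partial intake. Section 5.3 classes consenting patients who never start treatment as screen failures. PP also pushes caecal intubation upward, through its requirements for a completed colonoscopy and data on all segments.

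**5. Gas.** In phase II, 0/50 patients with dangerous levels would be compatible with a true rate of up to 1 − 0.025^(1/50) = 7.1%. In phase III, if neither arm had such a patient, the Newcombe interval for the difference is ±z²/(n+z²), with z² = 3.84. That is 3.84/351.84 = ±1.1 points at 348 per arm and 3.84/316.84 = ±1.2 points at 313 per arm. Wald would give 0 to 0. As a second illustration, 3 unsafe patients on mannitol against 1 on PEG, with 348 per arm, gives a difference in safe proportions with Newcombe limits of −2.2 to +0.9 points (Wald −1.7 to +0.6). These counts are illustrations, not forecasts.

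**The case against.** These are descriptive outputs. The only dose criterion with a numerical threshold is 75% adequate cleansing, where Wald performs adequately. Counts are reported in any case, so a reader can compute an exact interval; FAS adherence is produced as supportive even if PP leads. The formal phase III objective in Section 3 is to assess the safety of mannitol, not to test a gas hypothesis, so by-arm description is a legitimate choice. All of this stands and limits the weight of the point. It does not justify prescribing an interval known to fail near 100%, or leaving a declared comparison without one.

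A reader might infer four stronger things that the documents do not support.
- **That Wald breaks down in 79–97% of cases.** At the assumed rates that is the chance of 47 or more successes out of 50. It merges an upper limit slightly above 100%, which can be truncated, with the misleading zero-width case, whose probability is 9–32% per dose.
- **That PP adherence leads the dose choice by definition.** The PP sentence closes the Efficacy subsection and its reach is ambiguous.
- **That willingness to reuse has the same problem.** Nothing in the documents places it near 100%.
- **That the background gas studies forecast the counts.** Section 2.2.1 reports no elevated levels in 50 mannitol patients, but under minimal insufflation. The PEG hydrogen figure in Section 2.1 is per sample, not per patient. Neither matches this endpoint.

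**Conclusion.** The point holds as a should-fix on analysis wording. The failure of Wald at or near 50/50 is arithmetic. Its frequency is conditional: the 9–32% zero-width probability and the 91% to 68% coverage rest on an intubation rate of 95.2–97.7% that combines PEG failure rates with mannitol cleansing shares, and on 50 evaluable patients per dose. The PP set may be smaller, and its entry criteria push the rate upward. Phase II adherence lacks a sound lead population on either reading of the PP sentence. The phase III gas comparison announced in Section 2.1 has no planned interval, although less critical variables do. The primary non-inferiority analysis, the sample size and the 75% criterion are not affected.

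**What to change.** **Section 9.4.1, phase II.**
- Replace Wald with Clopper-Pearson intervals for single proportions. Wilson is acceptable, though its coverage can dip to about 90% (89.8% at a true rate of 98.8% with n = 45).
- State that adherence and caecal intubation are led by the FAS, as in phase III.
- Report by dose the number of randomized patients who took no study drug, and reconcile this with the screen-failure definition in Section 5.3.

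**Section 9.4.2.**
- Add a Clopper-Pearson 95% CI for the safe-gas proportion in each dose group or arm.
- For phase III, add a descriptive Newcombe or Miettinen-Nurminen 95% CI for the mannitol minus PEG difference, among Safety-set patients with gas measured, and report the number missing by arm. No test or margin is needed.

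Replacing Wald for the other phase III differences is optional.

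**Cost.** Wording and standard SAS options; no extra patients or data. Intervals near 0% or 100% become slightly wider, and Clopper-Pearson is conservative (coverage about 99% at the assumed intubation rates).

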1 PROTOCOL SUMMARY

1.1 SYNOPSIS

Protocol number	Mannitol_03-2018
Title of Study	Efficacy and safety of mannitol in bowel preparation: assessment of adequacy and presence of intestinal levels of hydrogen and methane during elective colonoscopy after mannitol or standard split 2-liter polyethylene glycol solution plus ascorbate – a phase II/III, international, multicentre, randomized, parallel-group, endoscopist-blinded, dose-finding/non-inferiority study
Sponsor	NTC S.r.l.
Investigational Sites	Phase II - dose finding: approximately 13 sites located in Italy, Germany and France. Phase II pharmacokinetic sub-study: approximately 5 sites located in Italy. Phase III - non-inferiority: approximately 50 sites located in Italy, Germany, Russia and France.
Study Objectives	
Phase II: Dose-finding/Pharmacokinetic sub-study
 
○ To determine the effective and safe dose of mannitol for adequate bowel cleansing to be used in the comparative non-inferiority phase of the study (phase III).○ To define the pharmacokinetic profile of the mannitol doses used in dose finding through a pharmacokinetic sub-study. 
Phase III: Non-inferiority
 
○ To demonstrate the non-inferiority of mannitol vs. standard split 2L PEG ASC (Moviprep®) in bowel cleansing for colonoscopy.○ To assess the safety and tolerability of mannitol.○ To assess the adherence to and acceptability of the bowel preparation with mannitol and Moviprep®.

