
- T_0 (baseline before mannitol self-administration)
- T_1 (1 hour \pm 5 min after completion of mannitol self-administration)
- T_2 (2 hours \pm 5 min after completion of mannitol self-administration)
- T_4 (4 hours \pm 10 min after completion of mannitol self-administration, before colonoscopy)
- T_8 (8 hours \pm 10 min after completion of mannitol self-administration, after colonoscopy)

If patients do not undergo all PK evaluations, the sub-study sample size will be increased to guarantee at least 8 PK evaluations for each assessment time.

Phase III-Non-inferiority

A parallel-group design will be implemented to test the non-inferiority of bowel cleansing with the mannitol dose selected in phase II against standard split 2L PEG ASC. Phase III will begin only once all data collected from phase II necessary for establishing the optimal mannitol dose have been analysed. The non-inferiority study will involve 696 subjects randomized in a 1:1 ratio to one of the two cleansing agents. Randomization is stratified by centre.

Study visits

In both phases, the study will consist of four visits:

Visit 1 (\leq 28 days before the day of colonoscopy): after signed written informed consent is obtained from the patient, information concerning demographics, medical history, concomitant medications and indications for colonoscopy will be collected in the electronic case report form (eCRF).

Visit 2 (\leq 7 days before the day of colonoscopy): to complete the verification of inclusion/exclusion criteria, a blood sample will be drawn to assess the haematological and chemical parameters of all patients and to perform a pregnancy test for women of childbearing potential. Assessments include a urinalysis and the measurement of vital signs (heart rate and blood pressure).

Visit 3 (\leq 7 days before the day of colonoscopy): if eligibility criteria are met, the BSFS will be administered (only in phase II), randomization will be performed, study drug will be dispensed and verbal and written instructions for its use will be provided. Patients will be given a form on which to indicate date and time of start and end of study drug self-administration.

More than one visit may take place on the same day.

Visit 4 (day of colonoscopy):

- Phase II - dose finding

A blood and urine sample will be collected 4 hours \pm 30 minutes and 8 hours \pm 30 minutes after the end of study drug self-administration.

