4.1.3 PHASE III

A parallel-group design will be implemented to test the non-inferiority of bowel cleansing with the mannitol dose selected in phase II against standard split 2-liter polyethylene glycol plus ascorbate solution (Moviprep®). Phase III will begin only once all data collected from phase II necessary for establishing the optimal mannitol dose have been analysed. The non-inferiority study will be conducted in 4 countries (Italy, Germany, Russia and France) and involve 696 subjects randomized in a 1:1 ratio to one of the two study drugs. Randomization will be stratified by centre.

Study visits

Phase III of the study consists of four visits:

Visit 1 (≤ 28 days before the day of colonoscopy): after signed written informed consent is obtained, information concerning demographics, medical history, concomitant medications and indications for colonoscopy will be collected in the electronic case report form (eCRF). The incidence of adverse events will be recorded.

Visit 2 (≤ 7 days before the day of colonoscopy): to complete the verification of inclusion/exclusion criteria, a blood sample will be drawn to assess the haematological and chemical parameters (including electrolyte levels) of all patients and to perform a pregnancy test for women of childbearing potential. Assessments include a urinalysis and the measurement of vital signs (blood pressure and heart rate). The incidence of adverse events will be recorded.

Visit 3 (\leq 7 days before the day of colonoscopy): if inclusion/exclusion criteria are met, randomization will be performed, study drug will be dispensed and verbal and written instructions for its use will be provided. The date and time of colonoscopy will be communicated and reported on a form given to the patient. On the same form, patients will indicate date and time of start and end of study drug self-administration. The incidence of adverse events will be recorded.

More than one visit may take place on the same day.

Visit 4 (day of colonoscopy):

A blood and urine sample will be collected at the following time points:

- 4 hours \pm 30 minutes after the end of study drug self-administration
- 8 hours \pm 30 minutes after the end of study drug self-administration

After completion of bowel preparation, prior to colonoscopy, patients will fill in the questionnaire on acceptability and adherence. The Bowel Cleansing Impact Review (BOCLIR) is also to be completed, but only by patients enrolled at Italian centres.

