9 STATISTICAL CONSIDERATIONS

9.1 SAMPLE SIZE DETERMINATION

The total number of patients to be enrolled is approximately 846; 150 patients (50 in each mannitol dose group) for phase II dose finding, and 696 patients (348 in each treatment group) for the phase III non-inferiority study. The population for phase III will not include the patients who participated in phase II.

Phase II - Dose finding

The sample size is based on the precision of the estimate within each treatment group, i.e. the 95% confidence interval of the proportion of patients in each treatment group with adequate bowel cleansing (BBPS total score ≥ 6 , with BBPS ≥ 2 for each segment).

The table below shows the precision of the estimate for different rates of adequate bowel cleansing with a sample size of 50 patients.

Rates of adequate bowel cleansing (%)	Estimate Precision (%) (i.e. 95% CI*)
75	± 12
80	± 11
85	± 10

* Confidence interval estimated through normal approximation of binomial distribution without continuity correction.

Phase II - Pharmacokinetic sub-study

The expected sample size (10 patients in each dose group) is based on feasibility criteria.

Phase III - non-inferiority

The sample size is based on the proportion of patients with adequate bowel cleansing (BBPS total score ≥ 6 , with BBPS ≥ 2 for each segment). When the sample size in each group is 313, a two-group large-sample normal approximation test of difference of proportions with a one-sided 0.025 significance level will have 80% power to reject the null hypothesis that the test preparation is inferior to the standard preparation in favour of the alternative hypothesis that the test proportion is not inferior to the standard preparation (the difference in success proportions, $\pi_T - \pi_S$, is -0.08 or farther from zero in the same direction), assuming that the expected difference in success proportions is 0 and the proportion of successes in the standard group is 0.85 (the success rate for Moviprep® as reported in Bisschops R. et al., 2019, Choi et al., 2018 and Kwon et al., 2016 varies from 85% to 89%).

A proportion of patients with adequate bowel cleansing 8% lower than the expected 85% for gold standard Moviprep® would give a 77% success rate for mannitol, which falls within the 70-88.5% range reported for PEG-ASC (Repici et al., 2012; Choi et al., 2018; Hassan et al., 2013).

Sample size for two-group test of equivalence in proportions (large equal n's)

Test significance level, α (one-sided)	0.025

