Standard proportion, π_S	0.85
Equivalence limit difference, $\pi_T - \pi_S, \Delta_0$	-0.08
Test expected proportion, π_T	0.85
Expected difference, $\pi_T - \pi_S, \Delta_1$	0
Power (%)	80
N per group	313

Sample size was computed based on normal approximation of binomial distribution without continuity correction

The non-inferiority margin $\pi_T - \pi_S = -0.08$ corresponds to a relative risk $\pi_T/\pi_S = 0.906$. Should the proportion of successes in the standard group be lower than 0.85, the non-inferiority margin will be adjusted in order to have a relative risk of at least 0.906 (e.g. if the proportion of successes observed in the standard group is 0.80, the non-inferiority margin $\pi_T - \pi_S$ will be set equal to = -0.075, corresponding to a relative risk equal to 0.906).

The total sample size (626) is adjusted to 696 patients (348 in each treatment group) considering an expected rate of dropouts and major protocol deviations of about 10% (using Freedman's formula (*Control Clin Trials*, 1990): $n' = 100*n/(100-x)$, where x is the expected percent dropout rate).

The correctness of the assumptions used to compute the sample size for phase III of the study will be re-evaluated at the end of phase II and, if needed, the sample size will be re-estimated.

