9.2 RANDOMIZATION

At Visit 3, all eligible subjects will be randomized via eCRF to one of the treatment groups according to the study phase. The Investigator or his/her delegate will confirm that the subject has fulfilled all the inclusion/exclusion criteria in the eCRF. The eCRF will assign a randomization number to the subject, which will be used to link the subject to the treatment and will specify a unique medication number for the package of study treatment to be dispensed to the subject. The subject's randomization number will not be shown in the eCRF: only the medication number will be made available.

For each phase of the study a stratified subject randomization list will be produced in balanced blocks through a validated SAS program.

Phase II – dose finding: the randomization will be stratified by centre and by the presence of constipation (yes/no), defined as the recurrent use of laxatives or Bristol Stool Form Scale (BSFS) < 3 in the two weeks before randomisation.

Phase III – non-inferiority: the randomization will be stratified by centre.

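### Phase III randomisation is stratified by centre but the primary non-inferiority interval ignores centre; a pooled centre-stratified interval would change power by about -0.1 to +2 points, depending on a centre spread the plan does not give

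*Combined protocol and SAP*

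**What the plan says.** Three places make centre the phase III stratification factor, and none names another: the synopsis ("Randomization is stratified by centre"), section 4.1.3 ("Randomization will be stratified by centre") and section 9.2 ("the randomization will be stratified by centre"). The synopsis expects "approximately 50 sites located in Italy, Germany, Russia and France".

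The primary analysis in section 9.4.1 is a two-tailed 95% confidence interval for the difference between two proportions: "The Wald method for non-inferiority of proportions will be applied". Its lower limit is compared with -0.08. If the observed standard-group rate is below 0.85, the margin is tightened to keep a relative risk of 0.906. The FAS and PP results count equally. No stratum, weight or covariate is named. Section 9.1 sizes the trial in the same way, with "a two-group large-sample normal approximation test of difference of proportions".

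Centre is analysed only in phase II, through logistic regression with pooling of centres if enrolment is unbalanced. Two clauses look ahead to phase III. Section 9.1 says the sample-size assumptions "will be re-evaluated at the end of phase II and, if needed, the sample size will be re-estimated". Section 9.4.1 says "the need to modify the stratification factors for phase III will be evaluated and the study protocol amended, if needed". Neither brings centre into the phase III interval.

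**The concern.** Stratifying the randomisation balances the arms within each centre. If success rates differ between centres, that balance removes part of the chance variation in the treatment difference. The crude Wald variance does not use this. It still counts the between-centre spread, so the interval is somewhat wider than it needs to be.

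Some spread is plausible, because diet and additional fluids follow local practice (section 6.1.2). Endoscopist training (section 4.1) is meant to limit it. Competitive enrolment (section 10.1.10) makes uneven centre sizes likely, which affects how a stratified analysis should be built.

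Only precision is at stake. No false non-inferiority claim and no patient risk follow from the crude interval.

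**Working it through.** **1. The plan's own figure (section 9.1).** Inputs: 0.85 in both groups, margin 0.08, one-sided 0.025, 80% power, no continuity correction.

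- n per group = (1.960 + 0.842)² × 2 × 0.85 × 0.15 / 0.08² = 312.7, so 313.
- Power at 313 per group is 80.03%.
- 626 / 0.9 = 695.6, so 696.

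All stated figures reproduce. There is no centre term, and 696 / 50 is about 14 randomised patients per centre.

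**2. Closed form for the gain.** Let ICC = SD² / (0.85 × 0.15), where SD is the between-centre standard deviation of the success rate. Stratifying reduces the variance by the factor (1 - ICC). At 313 per group the crude standard error is √(0.255/313) = 0.02854. At ICC 0.05 (SD 0.08) the true standard error is 0.02854 × √0.95 = 0.02782.

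- Crude power = Φ[(0.08 - 1.960 × 0.02854) / 0.02782] = 80.6%.
- Stratified power = Φ[0.08 / 0.02782 - 1.960] = 82.0%.
- Gain: 1.4 points. At ICC 0, 0.02, 0.08 and 0.10 the gain is 0, 0.5, 2.2 and 2.7 points.

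This is an upper guide, because it ignores the cost of many small strata.

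**3. Simulation, small centres pooled.** The stratified estimate is Σwₖ(p_Tk - p_Sk)/Σwₖ with wₖ = n_Tk·n_Sk/nₖ (Mantel-Haenszel) and the Sato variance. Assumptions:

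- 696 randomised in 50 centres of uneven size (gamma weights, shape 1.5), blocks of 4, 10% random exclusions.
- Beta-distributed centre rates with mean 0.85, equal in both arms within a centre.
- Centres with fewer than 15 evaluable patients pooled within four countries (20/12/10/8 centres), giving about 20 strata.
- The margin follows the 0.906 rule, applied to the crude observed standard-group rate.
- 60,000 trials per setting.

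| Centre SD | Wald power % | Stratified power % | Gain | Gain, margin fixed at -0.08 |
|---|---|---|---|---|
| 0 | 79.74 | 79.60 | -0.14 | -0.15 |
| 0.03 | 79.81 | 79.83 | +0.02 | 0.00 |
| 0.05 | 80.08 | 80.33 | +0.25 | +0.19 |
| 0.08 | 80.38 | 81.15 | +0.77 | +0.76 |
| 0.10 | 80.59 | 82.00 | +1.41 | +1.38 |
| 0.12 | 81.10 | 83.15 | +2.05 | +1.98 |

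The Monte Carlo standard error of a gain is 0.05 to 0.07 point. Smaller repeat runs gave -0.4 to 0.0 at SD 0, -0.2 to +0.4 at SD 0.05, +1.2 to +1.5 at SD 0.10 and +1.9 to +2.1 at SD 0.12. The tightened margin applied in about 48-49% of trials.

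Scale of the spread: one centre in ten has a true rate below 78% at SD 0.05, 71% at SD 0.10 and 68% at SD 0.12.

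Mean half-width at SD 0.10 is 5.57 (Wald) against 5.43 points (stratified). (5.57/5.43)² = 1.05, or about 5% more information.

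**4. One-sided error at a true difference of -0.08.**

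- Fixed margin: Wald 2.56% at SD 0, falling to 2.2% at SD 0.12; stratified 2.4-2.6%.
- Tightened margin: Wald 1.8-2.1%; stratified 2.0-2.2%.

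**5. Effect of the pooling rule (30,000 trials, tightened margin).**

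| Rule | Gain at SD 0.10 | Loss at SD 0 |
|---|---|---|
| Pool centres with <10 evaluable | +1.50 | 0.36 |
| Pool centres with <15 | +1.41 | 0.14 |
| Pool centres with <20 | +1.08 | 0.11 |
| Country strata only | +0.22 | 0.10 |

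With no pooling the loss at SD 0 is 0.85 point. A separate simulation without pooling (20,000 trials, fixed margin) agrees: -0.6 (equal centres) and -0.8 (uneven) at ICC 0, +0.7 for both at ICC 0.05, and +2.8 and +1.7 at ICC 0.10.

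**The case against.** The strongest reply is that nothing here is broken. Sample size and analysis share one unstratified framework. The crude interval is valid under stratified randomisation and, if centres differ, slightly conservative, which is no fault in a non-inferiority trial. On this view the proposal swaps one valid pre-specified interval for another. All of that stands, which is why the point is graded as an option.

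The benefit also rests on a spread that the documents do not give. At SD 0.05 or below it is about a quarter of a point at most, and its sign is uncertain. The 2-point figure needs a spread at which one centre in ten falls below 68%, and nothing in the documents shows this. That stands too, so the result has to be read as a range that includes a small loss.

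The gain depends on assumed details as well: block size, centre sizes, the country split and the pooling rule. Under these assumptions the rule of fewer than 15 evaluable patients pools about 67% of centres, holding about 35% of patients. The power runs assume no treatment-by-centre interaction. The stratified difference would also be compared with a margin set from a crude rate. These are real complications, but each can be settled in a sentence before lock, and the error runs that used the crude-rate margin stayed below 2.5%.

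The objection does not show that centre enters the phase III analysis anywhere, or that the change would cost more than a fraction of a point.

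**Conclusion.** The point holds as a low-priority improvement. Phase III is randomised by centre, and its primary interval does not use centre. With small centres pooled, a stratified interval would change power by about -0.1 to +2 points: roughly nothing at SD 0.05 or less, about 1.4 points at SD 0.10, and about 2 points only at SD 0.12. Planned power and error control are sound as they are.

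Confidence is moderate. That centre is left out is plain from the text, and the power figures were repeated with similar results. The between-centre spread, block size, centre-size distribution, country split, random exclusions and absence of interaction are all assumptions.

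**What to change.** In section 9.4.1 and the synopsis:

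- Pre-specify the Mantel-Haenszel risk difference stratified by centre, with Sato variance, as the primary estimate on both FAS and PP.
- Pool small centres within country by a rule fixed before database lock, for example fewer than 15 evaluable patients. Do not use country strata alone, which lose most of the gain.
- State that the stratified lower limit is compared with -0.08, or with the margin from the 0.906 rule when the crude observed standard-group rate is below 0.85.
- Use the same interval for the superiority reading.
- Keep the unstratified Wald interval as a pre-specified sensitivity analysis.

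The cost is protocol and SAP wording and a standard SAS procedure, with no extra patients or data. The downsides are a pooling rule to define, one sentence on the margin, and about 0.1 to 0.2 point of power lost if centres do not differ. If they do differ, the Wald interval's slight conservatism is given up, with one-sided error staying near 2.5%.
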